2. INVESTIGATION PLAN

2.1. Study Design and Randomization

This is a phase 2, randomized, double-blind, placebo-controlled, dose-ranging study to assess varying doses of SC and IV regimens of evinacumab in patients diagnosed with primary hypercholesterolemia (HeFH, or non-HeFH with a history of clinical ASCVD) who have an LDL-C ≥ 70 mg/dL (1.81 mmol/L) for those patients with clinical ASCVD and LDL-C ≥ 100 mg/dL (2.59 mmol/L) for those patients without clinical ASCVD, despite receiving a stable maximally-tolerated LMT. The LMT should include a stable, maximally-tolerated statin and stable PCSK9 inhibitor antibody for patients who are HeFH, or non-HeFH with a history of clinical ASCVD. Patients with HeFH not on a statin are eligible if there is documentation of

inability to tolerate at least 2 statins (see Protocol Section 7.3) Background Treatments for further information).

Patients who meet all inclusion criteria and who meet none of the exclusion criteria will be randomized within either Group A (1:1:1:1) or Group B (1:1:1) to receive:

Group A

- Evinacumab 300 mg SC QW for 16 weeks, or
- Evinacumab 300 mg SC Q2W, for 16 weeks (alternating with placebo on opposite weeks), or
- Evinacumab 450 mg SC QW, for 16 weeks, or
- Placebo SC QW, for 16 weeks

Group B

- Evinacumab 5 mg/kg IV Q4W, for 24 weeks, or
- Evinacumab 15 mg/kg IV Q4W, for 24 weeks, or
- Placebo IV Q4W, for 24 weeks

Enrollment of IV cohorts will occur before enrollment of SC cohorts, accordingly, enrollment of Group A will not begin until Group B enrollment is completed.

Patients enrolled to the SC (Group A) and IV (Group B) treatment groups will have different visit schedules because of the differences in dosing frequency.

Randomization will be stratified by high-intensity statin (Yes/No) and HeFH (Yes/No) at baseline. High-intensity statin is defined as rosuvastatin 20 mg or 40 mg daily, atorvastatin 40 mg or 80 mg daily, or simvastatin 80 mg daily (if already on this dose for >1 year). To ensure an adequate number of patients with HeFH are included in this study and exposed to each dose, randomization will be stratified 2:1 (HeFH:non-HeFH; 24:12) within each treatment group.

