5.7.1. Analysis of Primary Efficacy Variable

For the double-blind primary comparison of the evinacumab group to the placebo group, the percent change from baseline in calculated LDL-C at week 16 will be analyzed in the ITT population using a mixed-effect model with repeated measures (MMRM) approach. All post-baseline data available within week 2 to week 16 efficacy analysis windows will be used and missing data are accounted for by the MMRM model. Each model will include the fixed

categorical effects of treatment group (evinacumab dose regimens versus placebo), randomization strata (high-intensity statin [Yes/No] and HeFH status [Yes/No]), time point (weeks 2, 4, 6, 8, 12, 16 for the Group B treatment groups; weeks 2, 4, 6, 8, 10, 12, 14, 16 for the Group A treatment groups), treatment-by-time point interaction, and strata-by-time point interaction, as well as the continuous fixed covariates of baseline calculated LDL-C value and baseline value-by-time point interaction. Contrast and estimate statements will be used to assess the treatment effects (LS means with confidence intervals) and each dose regimen pairwise comparison to placebo (mean difference and p-values).

This model will be run separately for each route of administration (Group A or Group B, with Group B consisting of 3 dose regimens for the variability estimate) with an unstructured correlation matrix to model the within-patient errors. Parameters will be estimated using restricted maximum likelihood method with the Newton-Raphson algorithm. Denominator degrees of freedom will be estimated using Satterthwaite's approximation.

Let μ_0 and μ_1 be the population means of the percent change from baseline in calculated LDL-C at week 16 under each of 2 placebo control arms and the 4 evinacumab treatment arms, respectively. The hypothesis that will be tested is " $H_0: \mu_0 = \mu_1$ " versus " $H_1: \mu_0 \neq \mu_1$ ".

The 4 primary treatment group comparisons will evaluate at week 16 each evinacumab dose regimen to the placebo group corresponding to the route of administration (IV or SC).

1. Evinacumab 15 mg/kg IV Q4W compared to Placebo IV
2. Evinacumab 450 mg SC QW compared to Placebo SC
3. Evinacumab 300 mg SC QW compared to Placebo SC
4. Evinacumab 300 mg SC Q2W compared to Placebo SC

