10.5. Detailed Description of the Multiple Imputation Procedure

The following is a detailed description of the multiple imputation procedure which will be used for analysis of the secondary efficacy endpoints.

In general, the missing pattern is anticipated to be not monotone, a two-step approach will be used:

- Step 1: the MCMC method will be used in conjunction with the IMPUTE=MONOTONE option to create an imputed data set with a monotone missing pattern. Set the SEED=1643 option in SAS MI procedure
- Step 2: Using the monotone data set from step 1, missing data will be imputed using the regression method. Set the SEED=3461 option in SAS MI procedure

The imputation model for step 1 will include the treatment group and the values of the analyzed parameter at baseline and planned time-points up to week 24/week 16.

The imputation model for step 2 will include the same variables as in step 1 with the following additional variables:

- the randomization strata;
- age, BMI, and gender (age and BMI included as continuous variables).

Non-continuous variables included in the imputer's model (i.e., treatment group, randomization strata and gender) are not expected to be missing.

In addition, for continuous efficacy variables anticipated to have a non-normal distribution (i.e. TG and Lp(a)), data will be log-transformed before imputation process and then back-transformed to create the imputed data sets using the TRANSFORM statement of SAS MI procedure.

For variables other than those continuous efficacy variables anticipated to have a non-normal distribution (i.e. TG and Lp(a)), for each simulation leading to negative imputed value, another value will be redrawn using MINIMUM option of SAS MI procedure.

The number of imputations (100) will be informally verified by replicating sets of 100 imputations and checking whether the combined results are stable. If not stable, the number of imputations will be increased and informally checked as above, and thus continued until stable estimates are obtained.

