10.6. Detailed Description of Pattern Mixture Model

As a sensitivity analysis of the primary efficacy endpoint (i.e. percent change from baseline to Week 16 in LDL-C), a pattern-mixture model approach will be used, with a different imputation strategy applied for missing LDL-C values during the on-treatment period (i.e. within the time period from the first double-blind study treatment administration up to the day of the last double-blind study treatment administration +35 days or to the day before the first open-label study treatment administration, whichever comes first for Group B or +14 days for Group A) and missing LDL-C values after treatment discontinuation (i.e. after the day of last study treatment

administration +35 days for Group B or +14 days for Group A) based on the following assumptions:

- Patients within 35 days for Group B or 14 days for Group A of their last study treatment administration would continue to show benefit from treatment similar to that observed at the scheduled time point. Therefore, LDL-C values missing during the on-treatment period will be considered “Missing at Random” and imputed using a model estimated using all samples collected on treatment.
- Patients who stopped taking their study treatment no longer benefited from it in the future, and thus tended to have LDL-C values returning to baseline. Thus LDL-C values missing after treatment discontinuation will be imputed based on patient’s own baseline value.

The assumptions for this approach are based on the following considerations:

- Missing values during the on-treatment period are mostly consecutive to:
 - Visits performed outside of the pre-specified time-window
 - No blood sample available although visit was done
 - LDL-C not measurable due to technical reasons

In addition, these missing data are often intermittent, i.e. followed by LDL-C values collected at subsequent visits. It is therefore considered reasonable to assume that these missing data were “At Random”.

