Missing LDL-C values will be imputed 100 times to generate 100 complete data sets. The percent change from baseline to Week 16 will be derived from observed and imputed LDL-C at this time point. The completed data sets will be analyzed using an analysis of covariance (ANCOVA) model with treatment group and randomization strata as fixed effects, and the baseline LDL-C value as continuous covariate. The results from the 100 analyses will be combined using Rubin’s formulae. If necessary, the number of imputations (100) will be increased until stable estimates are obtained.

Imputation of missing data during the on-treatment period

Missing LDL-C values during the on-treatment period will be imputed from other on-treatment measurements assuming Missing At Random, using SAS® MI procedure.

Only LDL-C values collected during the on-treatment period will be included in the imputation model. This way, missing LDL-C values during the on-treatment period will be imputed based solely on observed on-treatment LDL-C values.

The imputation model will include the treatment arm, baseline LDL-C value, and all LDL-C values at pre-specified visits. Since the pattern of missing data will necessarily be non-monotone, a Monte-Carlo Markov Chain (MCMC) method will be used. A minimum value of 0 will be specified in order to avoid negative imputed LDL-C values.

A sample SAS code is provided below:

```
proc mi data=DATAIN out=DATAOUT nimpute=100 minimum=. 0 0 0 0 0 0 0 0 SEED=1643;
```

```
mcmc impute=monotone;  
var ARM LDL_BASE LDL_W2 LDL_W4 LDL_W8 LDL_W12 LDL_W16;  
run;
```

As stated above, the input dataset DATAIN will include only LDL-C values collected during the on-treatment period. Any LDL-C values collected during the post-treatment period will be excluded from the input dataset. In practice, the MI procedure will generate imputed values for all missing values (whether on-treatment or post-treatment), but only imputed values during the on-treatment period will be kept in the final datasets that will be analyzed using ANCOVA. Imputed values during the post-treatment period will be discarded and replaced by imputed values described in the next paragraph.

Imputation of missing data after treatment discontinuation

Missing LDL-C values during the post-treatment period will be imputed assuming LDL-C values would on average return to baseline values.

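### The sample code in SAP 10.6 does not carry out the imputation its text describes: one numeric arm column for three or four arms, planned visits left out, and week 16 never filled

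*SAP*

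**What the plan says.** SAP 10.6, text: "The imputation model will include the treatment arm, baseline LDL-C value, and all LDL-C values at pre-specified visits". Values missing on treatment are to be "imputed using a model estimated using all samples collected on treatment". On treatment means up to 35 days after the last double-blind dose in Group B and 14 days in Group A. Values missing later are drawn around the patient's own baseline instead.

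SAP 10.6, code: introduced with "A sample SAS code is provided below", it uses "mcmc impute=monotone" and the variable list "var ARM LDL_BASE LDL_W2 LDL_W4 LDL_W8 LDL_W12 LDL_W16". There is no BY statement and there are no arm indicators. MINIMUM holds one dot and eight zeros. The text after the code says the procedure will fill every missing value, on or off treatment.

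SAP 2.1: patients are "randomized within either Group A (1:1:1:1) or Group B (1:1:1) to receive" their regimens, so there are four arms in Group A and three in Group B.

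SAP 5.7.1 models weeks 2, 4, 6, 8, 12 and 16 for Group B, and weeks 2, 4, 6, 8, 10, 12, 14 and 16 for Group A. Of the MMRM it says: "This model will be run separately for each route of administration". Section 10.6 does not repeat this for the imputation.

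SAP 10.5, step 1, also uses monotone MCMC: "The imputation model for step 1 will include the treatment group and the values of the analyzed parameter at baseline and planned time-points". It gives no code and no arm coding, and it classes treatment group as a non-continuous variable. A second, regression step imputes what step 1 leaves.

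**The concern.** MCMC imputation treats every listed variable as jointly normal. A single numeric ARM column is harmless with two arms. With three or four, it fits a straight line through whatever numbers label the arms. The imputed arm means then depend on that labelling, which the SAP does not fix. The analysis that follows is an ANCOVA with treatment group as a fixed effect, so the imputation model is more restrictive than the model it feeds.

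The other mismatches need no assumption: the visit list is shorter than the text requires, MINIMUM does not match the variable list, and the monotone option cannot supply a missing week 16, which is the endpoint visit.

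At stake is whether this sensitivity analysis of the primary endpoint can be run as pre-specified, and whether its on-treatment imputations are free of an artefact of arm numbering.

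**Working it through.** **1. Planning figures.** The SAP gives no figure for the imputation model. Effect and spread come from SAP 2.2: means of 27% and 7%, read as reductions (−27 and −7), SD 25, two-sided 0.05, 90% power, 5% dropout. Normal formula: 2 × (1.96 + 1.2816)² × 25²/20² = 32.8, so 33 per arm. By the t-test, 34 per arm gives 90.2% power, and 34/0.95 = 35.8, so 36. The stated 36 reproduces.

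**2. Visits and list lengths.**

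| | Group A | Group B |
|---|---|---|
| Visits in SAP 5.7.1 | 8 | 6 |
| Visits in the code | 5 (2, 4, 8, 12, 16) | 5 (same) |
| Omitted | 6, 10, 14 | 6 |
| Variables needed (one arm column, baseline, visits) | 10 | 8 |
| Variables in the code | 7 | 7 |
| MINIMUM entries | 9 | 9 |

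**3. Gaps the code fills.** Monotone imputation fills a gap only when a later listed variable is observed, which is why SAP 10.5 adds a second step. Week 16 is last in the list.
- Week 4 missing, week 16 observed: week 4 is filled.
- Week 16 alone missing: nothing is filled.
- Weeks 4 and 16 missing: only week 4 is filled.

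**4. Misfit of one arm column, no other visit observed.** Least-squares line of arm means on arm code, equal n; misfit is fitted minus true.
- Group A, placebo = 0 and active arms 1 to 3, true −7, −27, −27, −27: fitted −13, −19, −25, −31; misfit −6, +8, +2, −4.
- Group B, placebo = 0, 5 mg/kg = 1, 15 mg/kg = 2, true −7, −27, −27: fitted −10.3, −20.3, −30.3; misfit −3.3, +6.7, −3.3. The 15 mg/kg versus placebo contrast has zero bias.
- Group B in listed order (5, 15, placebo = 1, 2, 3): that contrast is off by 6.7 + 3.3 = 10.
- If 5 mg/kg truly averages −17, dose order gives zero misfit in every arm.

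**5. Who would be imputed this way.** Using the SAP 10.2 windows and the dosing schedule:
- Group B: the week-16 window opens on day 99. A week-8 dose (57 + 35 = day 92) ends too early; a week-12 dose (85 + 35 = day 120) reaches it.
- Group A: the window opens on day 107. A week-13 dose (92 + 14 = day 106) misses it; a week-14 dose (99 + 14 = day 113) reaches it.

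A patient on schedule who is still on treatment in that window has therefore passed every earlier lipid visit.

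**6. Misfit given earlier visits.** Assume k earlier visits with equal correlation ρ and the full arm effect at each, working in percent change without baseline. Let R be the mean square of the step-4 misfits. The fraction of misfit that remains is

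SD²(1 − ρ) / [SD²(1 + (k − 1)ρ) + kR].

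Group A: R = (36 + 64 + 4 + 16)/4 = 30. With k = 4, as in the code, and ρ = 0.5: 312.5/(1562.5 + 120) = 0.186, and 0.186 × 8 = 1.49.

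| ρ (assumed) | Largest misfit, A | Largest misfit, B |
|---|---|---|
| 0.3 | 2.68 | 2.29 |
| 0.5 | 1.49 | 1.26 |
| 0.7 | 0.73 | 0.62 |
| 0.85 | 0.32 | 0.27 |

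If earlier visits carried only half the effect, the Group A figure would be 4.1 to 5.3.

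**7. Effect on results.** The on-treatment missing fraction is assumed to be 5% (range 2 to 10%); the SAP's 5% is a dropout rate.
- Arm mean, Group A: 0.05 × 2.68 = 0.13 at ρ = 0.3, and 0.05 × 0.32 = 0.02 at ρ = 0.85. At ρ = 0.3 the range over 2 to 10% missing is 0.05 to 0.27.
- Largest contrast with placebo, Group A, ρ = 0.3: 2.68 − (−2.01) = 4.69 per imputed value, and 0.05 × 4.69 = 0.23. The standard error is 25 × √(2/36) = 5.9.

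**8. With arm indicators** the arm means are unconstrained and this misfit is zero under any numbering.

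**The case against.** The code is labelled a sample. The prose never asks for numeric coding, SAP 10.5 calls treatment group non-continuous, and a careful programmer would probably put this right. That lowers the risk but does not remove the defect: no other coding is stated anywhere. Where 10.6 does intend estimation within arm, for the post-treatment variance, it says so.

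Run verbatim, the code imputes no missing week 16, so there is nothing there for the arm column to bias. This stands. It is a second fault in the same block, and repairing it alone would bring the arm coding into play.

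A reader might infer errors of 8 to 10 points per imputed week-16 value. Those figures need a patient on treatment in the week-16 window with no post-baseline LDL-C, and step 5 shows that essentially does not arise on schedule. Bias is not certain either: it depends on the true means and the codes, and it can vanish for 15 mg/kg IV versus placebo.

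A reader might also infer that the primary result is at risk, or that this is its only missing-data check. The MMRM takes treatment as categorical and does not use these imputations. SAP 5.7.1.1 also plans a tipping-point and an on-treatment analysis.

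Nor does SAP 10.5 prescribe a numeric arm. Its step 1 fills only intermittent gaps, and a missing week 16 after the last observed value comes from step 2. Any effect on the tipping-point, TG, Lp(a) and binary analyses is indirect.

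**Conclusion.** The point holds as a specification error with small expected numerical effect. Three mismatches rest on the text and code alone: the omitted visits, the MINIMUM length, and the unfilled week 16. The single arm column is the wrong model for three or four arms unless their means happen to be linear in the codes.

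If week 16 is repaired and the arm column kept, the largest misfit is roughly 0.3 to 3 points per imputed value, in a direction set by the coding. At 5% imputed, an arm mean moves by about 0.1 point. This assumes the planning means and SD, equal between-visit correlation of 0.3 to 0.85, and the full effect at four earlier visits. With only half the effect at those visits, the arm mean could move by 0.05 × 5.3 = 0.27 point.

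A changed conclusion is unlikely. The effect is confined to the pattern-mixture analysis and, indirectly, analyses that use step 1 of SAP 10.5. The primary MMRM is unaffected.

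**What to change.** - In SAP 10.6 and step 1 of SAP 10.5, state that imputation is run separately by route, with arm as indicator variables: three for Group A, two for Group B.
- In VAR, list every visit of the route at which the parameter is planned to be measured. For LDL-C through week 16 this gives 3 + 1 + 8 = 12 variables for Group A and 2 + 1 + 6 = 9 for Group B. Give MINIMUM one entry per variable in the same order.
- In SAP 10.6, use full MCMC imputation, or add the second step of 10.5, so that a missing week 16 is imputed.

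Indicators are preferable to imputing within each arm. In Group A, baseline plus eight visits needs 9 × 10/2 = 45 covariance parameters, which is thin for about 36 patients per arm.

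The cost is SAP wording and a few code lines. No data collection or sample size changes.

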10.4.3. Efficacy Analyses

10.4.3.1. Primary Efficacy Analysis

For the double-blind primary efficacy analysis, the percent change from baseline in calculated LDL-C at week 16, as defined in Section 4.2, will be analyzed in the ITT population using a mixed-effect model with repeated measures (MMRM) approach. All post-baseline data available within week 2 to week 16 analysis windows will be used and missing data are accounted for by the MMRM model. Each model will include the fixed categorical effects of treatment group (placebo and evinacumab dose regimens), randomization strata, time point (weeks 4, 8, 12, 16 for the Group B treatment groups; weeks 2, 4, 6, 8, 12, 16 for the Group A treatment groups), strata-by-time point interaction, and treatment-by-time point interaction, as well as the continuous fixed covariates of baseline LDL-C value and baseline value-by-time point interaction. Contrast and estimate statements will be used to assess the treatment effects (LS means with confidence intervals) and each dose regimen pairwise comparison to placebo (mean difference and p-values).

This model will be run separately for each route of administration (Group A or Group B, with Group B consisting of 3 dose regimens for the variability estimate) using an unstructured correlation matrix to model the within-patient errors. Parameters will be estimated using a restricted maximum likelihood method with the Newton-Raphson algorithm. Denominator degrees of freedom will be estimated using Satterthwaite's approximation.

The 4 primary treatment group comparisons will evaluate at week 16 each evinacumab dose regimen to the placebo group corresponding to the route of administration (IV or SC).

1. Evinacumab 15 mg/kg IV Q4W compared to Placebo IV
2. Evinacumab 450 mg SC QW compared to Placebo SC
3. Evinacumab 300 mg SC QW compared to Placebo SC
4. Evinacumab 300 mg SC Q2W compared to Placebo SC

The statistical testing of the 4 pairwise comparisons for the primary measure will be evaluated at a 2-sided significance level of 0.05 per pair wise comparison, adjusting for multiplicity through a hierarchical inferential approach.

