1.2.3. Modifications from the Statistical Section in the Final Protocol

The summary of modifications is listed in the following table.

Item	Protocol Section	Description
1	10.3.1.1 Intent-to-Treat (ITT)	SAP Section 3.1.1 Evaluable primary endpoint requirement for the primary analysis population was removed per FDA request.
2	10.3.2.1 Double-Blind Safety Analysis Set/second item “For patients receiving study drug from more than 1 treatment group during the trial, the treatment group allocation for as-treated analysis will be the one in which the patient was treated with the highest number of injections (Group A) or infusions (Group B).”	SAP Section 3.2: The second item for determining the as-treated treatment group will be conservatively changed to: “For randomized patients receiving both evinacumab and placebo study treatment during the trial, the treatment group allocation for as-treated analysis will be evinacumab.
3	10.4.3.1 Primary Efficacy Analysis “Each model will include the fixed categorical effects of treatment group (placebo and evinacumab dose regimens), randomization strata, time point (weeks 4, 8, 12, 16 for the Group B treatment groups; weeks 2, 4, 6, 8, 12, 16 for the Group A treatment groups)”	SAP Section 5.7.1 Timepoints in the MMRM model are updated: “Each model will include the fixed categorical effects of treatment group (evinacumab dose regimens versus placebo), randomization strata (high-intensity statin [Yes/No] and HeFH status

Item	Protocol Section	Description
		[Yes/No]), time point (weeks 2, 4, 6, 8, 12, 16 for the Group B treatment groups; weeks 2, 4, 6, 8, 10, 12, 14, 16 for the Group A treatment groups)”
4	4.2.2. Secondary Efficacy Analysis 
 • Proportion of patients with calculated LDL-C < 100 mg/dL (2.59 mmol/L) at week 16 • Proportion of patients with calculated LDL-C < 70 mg/dL (1.81 mmol/L) at week 16 	SAP Section 4.7.2 These two secondary endpoints were removed due to the protocol amendment for changes to the inclusion criteria. Specifically, the LDL-C threshold was lowered to aid patient enrollment, potentially allowing patients to achieve one or both of the secondary endpoints at baseline.

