 3. Calculated LDL-C available at week 12 but missing at week 14,
 4. Calculated LDL-C available at week 10 but missing at week 12,
 5. Calculated LDL-C available at week 8 but missing at week 10,
 6. Calculated LDL-C available at week 6 but missing at week 8,
 7. Calculated LDL-C available at week 4 but missing at week 6,
 8. Calculated LDL-C available at week 2 but missing at week 4

9. Calculated LDL-C missing at week 2.
- Group B
 10. Calculated LDL-C available at week 16 (i.e. primary efficacy endpoint available),
 11. Calculated LDL-C available at week 12 but missing at week 16,
 12. Calculated LDL-C available at week 8 but missing at week 12,
 13. Calculated LDL-C available at week 6 but missing at week 8
 14. Calculated LDL-C available at week 4 but missing at week 6
 15. Calculated LDL-C available at week 2 but missing at week 4
 16. Calculated LDL-C missing at week 2.

A graph of mean percent change from baseline calculated LDL-C levels \pm SE at baseline, and at time points (weeks 4, 8, 12, 16 for the Group B treatment groups; weeks 2, 4, 6, 8, 12, 16 for the Group A treatment groups) will be provided by missing data pattern, for each treatment group.

- In the ITT population, demographic and baseline lipids will be described within the missing data pattern number 1 above versus the remaining missing data patterns above. P-values from Fisher exact test for categorical data and from asymptotic one-way ANOVA test for Wilcoxon scores (Kruskal-Wallis test) for continuous data, will be also provided, for descriptive purposes.

Tipping point analysis

Robustness of the primary analysis results to departure from the MAR assumption will be explored in the ITT population using the tipping point approach. For the tipping point approach, missing calculated LDL-C will be imputed using the multiple imputation method described in Appendix 10.5. All observed LDL-C values up to and including week 16 will be used, regardless of adherence to treatment and subsequent therapies (ITT estimand).

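### SAP 10.6 contradicts itself on which visits feed the pattern-mixture imputation, and the missing-pattern graph in 5.7.1.1 still uses superseded time points

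*SAP*

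**What the plan says.** **Primary model.** Protocol 10.4.3.1 listed the MMRM time points as "weeks 4, 8, 12, 16 for the Group B treatment groups; weeks 2, 4, 6, 8, 12, 16 for the Group A treatment groups". SAP 1.2.3 item 3 replaces that list ("Timepoints in the MMRM model are updated"). SAP 5.7.1 now has "time point (weeks 2, 4, 6, 8, 12, 16 for the Group B treatment groups" and "weeks 2, 4, 6, 8, 10, 12, 14, 16 for the Group A treatment groups". These are all the post-baseline core lipid panel visits up to week 16 in the schedules of events (SAP 10.7, Tables 3 and 4).

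**Pattern-mixture model.** SAP 10.6 states: "The imputation model will include the treatment arm, baseline LDL-C value, and all LDL-C values at pre-specified visits". It then says "A sample SAS code is provided below", and the code names the variables as "var ARM LDL_BASE LDL_W2 LDL_W4 LDL_W8 LDL_W12 LDL_W16". There is one list, with no separate version for Group A. The MINIMUM option in the same code is a dot followed by eight zeros.

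**Missing-pattern graph.** SAP 5.7.1.1 defines missing-data patterns visit by visit, using every lipid visit in each group. It then asks for a graph of mean percent change at baseline and at the protocol's old time points. For Group A these are "weeks 2, 4, 6, 8, 12, 16 for the Group A treatment groups) will be provided by missing data pattern"; for Group B they are weeks 4, 8, 12 and 16.

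**The concern.** The SAP deliberately moved the primary analysis to all lipid visits, but two supporting pieces for the same endpoint do not clearly follow.

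The pattern-mixture model exists to probe the missing-at-random assumption behind the MMRM. Its on-treatment imputation should therefore condition on at least the values the MMRM uses. SAP 10.6 leaves this open: a programmer following the sentence and a programmer following the code would run different analyses. Under the code, the observation closest to a missing week 16 in Group A would be set aside.

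The graph is meant to show how patients looked before their data stopped. For some patterns it omits exactly that last value.

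**Working it through.** The plan gives no figure on this point to reproduce, so the check compares the lists and then illustrates the size.

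**1. Post-baseline weeks in each place**

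| | Group A | Group B |
|---|---|---|
| MMRM, SAP 5.7.1 | 2, 4, 6, 8, 10, 12, 14, 16 | 2, 4, 6, 8, 12, 16 |
| Sample code, SAP 10.6 | 2, 4, 8, 12, 16 | 2, 4, 8, 12, 16 |
| Missing from code | 6, 10, 14 | 6 |
| Graph, SAP 5.7.1.1 | 2, 4, 6, 8, 12, 16 | 4, 8, 12, 16 |
| Missing from graph | 10, 14 | 2, 6 |

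**2. MINIMUM list.** It has 1 + 8 = 9 entries. The printed variable list has 7 (arm, baseline, five weeks). The full lists would need 2 + 6 = 8 for Group B and 2 + 8 = 10 for Group A. Nine entries fit none of these.

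**3. Who is affected if the code is run as printed.** The list matters only for values missing on treatment; later missing values are drawn around the patient's own baseline. In Group A the on-treatment period ends 14 days after the last dose, and the week-16 efficacy window is days 107 to 126 (SAP 10.2). On nominal dosing days:
- last dose at week 13 (day 92): 92 + 14 = 106, before the window opens;
- last dose at week 14 (day 99): 99 + 14 = 113, inside the window;
- last dose at week 15 (day 106): 106 + 14 = 120, inside the window.

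So the issue concerns a missing week 16 in Group A patients last dosed around weeks 14 to 15.

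**4. Possible size (correlations assumed; the documents give none).** The measure is the residual variance of week 16, as a share of its total variance, given the earlier values.

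- *Serial correlation r per 2 weeks.* Only the nearest earlier visit matters. With week 14 it is 1 − r²; with week 12 as the nearest it is 1 − r⁴. The ratio is 1 + r².
  - r = 0.8: 0.36 against 0.59 (64% larger)
  - r = 0.9: 0.19 against 0.34 (81% larger)
  - r = 0.95: 0.10 against 0.19 (90% larger)
- *Equal correlation r, with k predictors including baseline.* It is (1 − r)(1 + kr)/(1 + (k − 1)r). In Group A, k = 8 for all visits and k = 5 for the code.
  - r = 0.5: 0.556 against 0.583 (5% larger)
  - r = 0.8: 0.224 against 0.238 (6% larger)
- *Group B.* Week 12 is the nearest earlier visit in both lists, so serial correlation gives no loss. Equal correlation (k = 6 against 5) gives 0.571 against 0.583 at r = 0.5 and 0.232 against 0.238 at r = 0.8, a loss of 2 to 3%.

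**5. The graph.** Reading each pattern by its last value, seven in Group A (weeks 14, 12, 10, 8, 6, 4, 2) and five in Group B (weeks 12, 8, 6, 4, 2) end before week 16: 7 + 5 = 12. The last value is unplotted for patterns 2 and 4 (Group A, weeks 14 and 10) and patterns 13 and 15 (Group B, weeks 6 and 2), so 4 of 12. Pattern 15 keeps only its baseline point, where percent change is zero by definition.

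**6. The monotone option.** SAP 10.5 uses impute=monotone only to create a monotone missing pattern, followed by a regression step that fills the rest. A patient with every value except the final week 16 already has a monotone pattern. The 10.6 code uses the same option with no second step, although its text expects all missing values to be imputed.

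**The case against.** The strongest reply is that the code is labelled a sample and the sentence before it governs. Another sentence in 10.6 also bases the on-treatment model on all samples collected on treatment. Under that text, weeks 6, 10 and 14 are in the model. This stands. A reader might infer that the SAP has decided to impute week 16 in Group A without week 14, leaving week-14-dependent missingness uncovered. The documents do not support that; they show a text and a code example that disagree.

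A reader might also infer that the code's list is left over from the protocol. It is not: it omits week 6, which the protocol had for Group A, and includes week 2, which the protocol did not have for Group B. Only the graph repeats the old list.

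Other limits also stand:
- SAP 10.6 expects on-treatment gaps to be mostly out-of-window visits, absent samples or technical failures, often intermittent.
- The pattern-mixture analysis already differs from the MMRM in other ways: a week-16 ANCOVA, on-treatment values only, and no strata in the imputation model. Matching the visits would not make return to baseline the sole source of any difference.
- Departure from missing at random is also tested by the tipping-point analysis, which imputes under SAP 10.5 with all planned time points.
- The graph is descriptive, and 8 of the 12 patterns keep their last value.

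The reply does not remove the need for a correction. The code is the only place in 10.6 that names the visits, its MINIMUM list fits no version of the plan, and the graph's time points are body text, not sample code.

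**Conclusion.** The point holds as a consistency correction with two parts.

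First, SAP 10.6 contradicts itself on whether weeks 6, 10 and 14 (Group A) and week 6 (Group B) enter the imputation, and the code could not be used as printed. If it were, the consequence would be confined to on-treatment missing week-16 values, mainly in Group A patients last dosed around weeks 14 to 15. The documents do not allow its size to be determined. Under assumed correlations, the residual variance of such a value is between 5% and 90% larger in Group A, depending almost entirely on the correlation structure, and at most about 3% larger in Group B. Because few values should qualify, the effect on the pooled result is probably small.

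Second, the graph in 5.7.1.1 uses superseded time points and loses the last observation in 4 of 12 patterns. This part needs no assumption beyond reading the patterns by last value.

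It would be wrong to conclude that the primary result or the missing-data strategy as a whole is compromised. The primary MMRM, the tipping-point analysis and the secondary-endpoint imputations are unaffected.

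**What to change.** - **SAP 5.7.1.1:** plot the missing-pattern means at the Section 5.7.1 time points. This adds weeks 10 and 14 for Group A and weeks 2 and 6 for Group B.
- **SAP 10.6, lists:** print two variable lists. Group B: arm, baseline, weeks 2, 4, 6, 8, 12, 16. Group A: arm, baseline, weeks 2, 4, 6, 8, 10, 12, 14, 16. Give MINIMUM lists of matching length (8 and 10 entries).
- **SAP 10.6, method:** either add the second regression step described in 10.5 or use full MCMC imputation, so that a missing final week-16 value is actually imputed. Extending the lists alone would not ensure this.

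The cost is a few lines of code and a sentence or two of SAP text, made before database lock. No new data are needed.
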